4. STUDY DESIGN AND METHODS

4.1. Study design

This is a randomized, open-label, parallel-arm study to investigate the efficacy and safety of pamrevlumab in patients with documented SARS-CoV-2 infection. The study consists of screening, a treatment period, and a follow-up period.

The study will enroll patients who have been hospitalized and who are not currently on invasive mechanical ventilation. The treatment period is open ended, and patients will be randomized to treatment with pamrevlumab or standard of care in a 1:1 ratio according to a pre-generated randomization list. Pamrevlumab dosing, 30 mg/kg IV, will be administered at day 1, day 7 and day 14. Day 1 is defined as the day of randomization which must also include administration of the first dose of pamrevlumab for patients in the active treatment arm.

Based on Investigator's decision, treatment may be continued every 3 weeks after day 14, up to 11 weeks.

Since the treatment scheme of pamrevlumab for this study is more intense as compared to previous studies conducted in IPF patients, as a further safety measure the first 3 patients randomized to receive the experimental drug will be treated one at a time, leaving a 1-week observation period between them.

A follow-up by visit or phone call will be performed 8 and 12 weeks after the end of the last dose of treatment. The treatment period for an individual patient will not exceed 11 weeks. The end of the study is defined as last patient last follow-up visit/phone call.

The study design has a total sample size of approximately 68 patients and consists of two stages. At the end of Stage 1 (Stage 1 requires 23 patients on pamrevlumab treatment arm), analyses of efficacy and safety will take place with a potential to stop the study for futility or for efficacy. A data

review committee composed of experts in respiratory medicine and intensive care will be involved in study oversight and interpretation of the study results. In patients showing worsening of clinical condition, independently of the treatment arm, the Investigator is free to introduce any therapy considered necessary.

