4.3. Diagnosis and main criteria for inclusion

Eligible patients are those with documented COVID-19, age \geq 18 to \leq 80 years with interstitial pneumonia (findings of consolidation or ground glass opacities as assessed by chest HRCT) and respiratory distress, defined as PaO₂/FiO₂ ratio of \geq 100 \leq 300 mmHg, requiring supplemental oxygen and hospitalization.

Exclusion criteria for the study are the following:

- Invasive mechanical ventilation at screening;
- Pregnancy;
- Incapacity to express a valid informed consent;
- Known hypersensitivity to monoclonal antibodies used as experimental drugs for any clinical indication.

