4.6. Determination of sample size

This study's sample size is based on Simon's two-stage design (Simon, 1989) on the pamrevlumab arm. For futility testing of Stage 1 of the study, a responder rate definition will be evaluated. Patients randomized to receive pamrevlumab are considered responders if the total number of days on ventilation is \leq 15 days after first dose of pamrevlumab and the patient is alive.

Key assumptions for sample size calculation include the following: (1) type I error rate, α (one-sided): 0.05; (2) power: 90%; (3) response probability of standard of care: 40%; (4) response probability of standard of care + pamrevlumab: 65%.

The null hypothesis that the true response rate is 40% will be tested against a one-sided alternative. In Stage 1, 23 patients will be accrued in pamrevlumab arm. If there are 9 or fewer responses in

these 23 patients, the study may be stopped. Otherwise, 11 additional patients will be accrued for a total of 34 in pamrevlumab treatment group. The null hypothesis will be rejected if 18 or more responses are observed in 34 patients on the pamrevlumab arm. This design yields a type I error rate of 0.05 and power of 90% when the true response rate is 65%.

The study will enroll approximately 50 patients in Stage 1 who will be randomized in 1:1 fashion (pamrevlumab vs. standard of care).

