4.7. Statistical methods

For futility testing in Stage 1, a responder rate definition will be used. Patients randomized to receive pamrevlumab are considered responders if the total number of days on ventilation is \leq 15 days after the first dose of pamrevlumab. In addition, chest HRCT scans obtained at enrollment and day 14 \pm 2 will used as supportive analyses in the assessment of futility.

Analysis of continuous endpoints will be conducted using analysis of covariance (ANCOVA) model with baseline value as a covariate and relevant baseline prognostic factors as other covariates.

Analysis of categorical endpoints will be conducted using either Fishers Exact test or Cochran-Mantel-Haenszel test comparing the categories between the two treatment arms.

Analysis of the time to mechanical ventilation, time to all-cause mortality, and time to hospital discharge, respectively, will be undertaken by plotting Kaplan-Meier curves. Hazard ratios will be estimated using the Cox proportional hazards model and these will be presented together with 95% two-sided confidence intervals. Other statistical methods will be applied, as appropriate.

5. Subject withdrawal criteria

Subjects may withdraw from the study at any time, for any reason. Reasons for discontinuing study drug treatment, as well as reasons for withdrawing from study, will be captured on CRF.

Reasons for withdrawing the subject from the study may include the following:

- 5.1. Any safety concern in the Investigator's opinion, that precludes further study participation
- 5.2. Pregnancy
- 5.3. Withdrawal of Consent

6. Pamrevlumab: storage, preparation and use

Pamrevlumab is a fully human IgG1 kappa monoclonal antibody that binds to CTGF and is formulated as solution for administration by IV infusion.

Pamrevlumab is supplied in single-use glass vials containing sterile, preservative-free solution 10 mg/ml pamrevlumab. The solution is composed of 10 mg/mL pamrevlumab, 1.60 mg/mL L-histidine, 3.08 mg/mL L-histidine HCl, 8.01 mg/mL sodium chloride, and 0.05 mg/mL polysorbate 20, resulting in a solution with a tonicity of approximately 290 mmol/kg and a pH of 6.0.

Vials of pamrevlumab must be stored refrigerated (2°C to 8°C), in a temperature- controlled and monitored environment, protected from light, and in a securely locked area to which access is limited to appropriate study personnel. Documentation of the storage conditions must be maintained.

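### Section 4.7 lets the binary primary endpoint be compared by an unadjusted Fisher exact test, which has less power than a CMH test stratified by the PaO2/FiO2 class already on record

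*Protocol*

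**What the plan says.** Section 4.7 on categorical endpoints: "Analysis of categorical endpoints will be conducted using either Fishers Exact test or Cochran-Mantel-Haenszel test comparing the categories between the two treatment arms". No stratification variable is given for CMH and nothing says when each test applies. The sentence just before it gives continuous endpoints an ANCOVA with the baseline value and relevant prognostic factors.

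Section 3.1 defines the primary endpoint as a proportion, so its between-arm comparison falls under the categorical sentence.

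Section 4.3 admits PaO2/FiO2 from 100 up to "300 mmHg, requiring supplemental oxygen and hospitalization". Section 3.3.1 divides that range into mild (above 200 to 300) and moderate (above 100 to 200); a value of exactly 100 falls in its severe class. The schedule in Section 9 records PaO2/FiO2 at screening and on day 1.

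Section 4.1 has patients "randomized to treatment with pamrevlumab or standard of care in a 1:1 ratio according to a pre-generated randomization list" and names no stratum.

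Section 4.6 sizes the trial on the pamrevlumab arm alone, with "1) type I error rate, α (one-sided): 0.05; (2) power: 90" percent.

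**The concern.** A severity measure that the protocol itself divides into classes is known for every patient at entry, because eligibility depends on it. The protocol uses baseline information for continuous endpoints but does not commit to using it for the primary endpoint. It goes further than silence, since it expressly permits a test that ignores severity and is conservative at this sample size.

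Two things are at stake. First, the randomised comparison has only modest power for the protocol's own target effect, and Fisher lowers it further. Second, the choice between two tests that can reach different verdicts is left open in an open-label trial. At 34 per arm and 40% versus 65%, Fisher and even an unstratified CMH disagree on significance in about 7% of trials two-sided and 9% one-sided.

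**Working it through.** **Inputs from the protocol.** About 68 patients at 1:1, so 34 per arm (4.1, 4.2); response 40% on standard of care and 65% on pamrevlumab (4.6); one-sided 0.05 for the single-arm rule (4.6). Section 4.7 sets no level or sidedness for the between-arm test, so both one-sided and two-sided 0.05 are shown.

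**Assumptions, not in the protocol.** Half the patients are mild. The mild-minus-moderate gap in response is 0 to 50 points, the same in both arms. CMH is used without continuity correction.

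**Step 1: the plan's own figure.** Section 4.6 states: "This design yields a type I error rate of 0.05 and power of 90% when the true response rate is 65" percent. With X1 ~ Bin(23, p) and X2 ~ Bin(11, p), the printed rule rejects with probability P(X1 ≥ 10 and X1 + X2 ≥ 18). This is 0.086 at p = 0.40 and 94.7% at p = 0.65. A cut-off of 19 gives 0.0443 and 90.0%. So the printed cut-off does not reproduce the stated figures, which is a separate matter. Either way this is a one-arm test against a fixed 40%, and the choice between Fisher and CMH does not enter it.

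**Step 2: Fisher at 34 per arm (exact).** Power is the sum of Bin(34, 0.40) × Bin(34, 0.65) probabilities over all tables with p ≤ 0.05.
- Two-sided: power 44.0%, actual type I error at 40% in both arms 0.030.
- One-sided: power 60.3%, actual type I error 0.031.

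**Step 3: unstratified CMH (score test).** With x responders on pamrevlumab and m in total, z = (x − m/2) / √[34·34·m(68 − m) / (68²·67)]. Power is 51.5% two-sided and 69.5% one-sided; type I error is about 0.05.

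**Step 4: stratified CMH (simulation, unstratified allocation).** Over the two classes h, z = Σ(a_h − n_Th·m_h/N_h) / √Σ[n_Th·n_Ch·m_h(N_h − m_h) / (N_h²(N_h − 1))], where a_h is responders on pamrevlumab, n_Th and n_Ch the arm sizes, m_h all responders and N_h all patients in class h. Response by class is 40% ± gap/2 on control and 65% ± gap/2 on pamrevlumab. Type I error is 0.048 to 0.052. Differences are taken before rounding.

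| Gap (points) | Control mild / moderate | Two-sided power | vs Fisher | vs unstratified CMH | One-sided power | vs Fisher | vs unstratified CMH |
|---|---|---|---|---|---|---|---|
| 0 | 40 / 40 | 53% | +9 | +2 | 67% | +7 | −2 |
| 20 | 50 / 30 | 56% | +12 | +4 | 68% | +8 | −1 |
| 30 | 55 / 25 | 58% | +14 | +7 | 70% | +10 | +1 |
| 40 | 60 / 20 | 62% | +18 | +10 | 74% | +14 | +4 |
| 50 | 65 / 15 | 68% | +24 | +16 | 79% | +19 | +10 |

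These figures can move by about a point with the random seed and with how the gap is modelled.

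**Step 5: splitting the gain.** At a gap of 30, the two-sided gain over Fisher is 58 − 44 = 14 points. At a gap of 0, where severity predicts nothing, it is already 53 − 44 = 9 points. So about 9 of the 14 points owe nothing to severity.

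**Step 6: chance imbalance.** With half the patients mild, the arms differ by 5 or more mild patients (about 15 points) in about 27% of trials and by 7 or more (about 20 points) in about 11%. Conditional on exactly 34 mild patients, the figures are 23% and 9%. A 20-point imbalance with a 40-point gap shifts the observed difference by 0.20 × 40 = 8 points. The standard error of that difference is √(0.40·0.60/34 + 0.65·0.35/34) = 0.117, about 12 points.

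**Step 7: stratifying the list.** Repeating step 4 with equal class numbers in each arm changes CMH power by at most about 2 points.

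**The case against.** The best case against the point is that CMH strata and list construction routinely sit in an SAP or a randomisation specification, neither of which is at hand. Section 4.7 already permits CMH, and Section 4.1 does not say that the list is unstratified. This stands as regards the list. It does not dispose of the test, because the protocol affirmatively allows Fisher, and stratified CMH has more power than Fisher at every gap examined.

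A reader might infer that severity can confound the result. The documents do not support that: allocation is randomised, so only chance imbalance remains. It can favour either arm, the test's error rate already covers it, and Fisher's type I error stays below 0.05.

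A reader might also credit the full 14-point two-sided gain at a 30-point gap, or 18 at 40, to severity adjustment. Step 5 shows otherwise. At one-sided 0.05, the only level that the protocol sets, stratifying is worth nothing against an unstratified CMH until the gap exceeds about 30 points, and it costs 1 to 2 points at gaps of 0 to 20. The protocol gives neither response rates by class nor the mild share, so the true gap is unknown.

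Finally, a reader might think that the stated 90% power is affected. It is not, because it belongs to the single-arm rule in 4.6.

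**Conclusion.** The point holds as one of efficiency and of leaving the primary test open. Permitting Fisher gives up about 9 to 24 points of two-sided power, or 7 to 19 one-sided, against CMH stratified by PaO2/FiO2 class, at 34 per arm and 40% versus 65%. The lower end of each range is Fisher's conservatism and does not depend on severity. The rest depends on an assumed gap of up to 50 points with half the patients mild. It is not a finding of bias, of inflated type I error, or of a fault in the randomisation list. A change is worth making because it is almost free and the permitted test is the weaker one throughout.

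**What to change.** In 4.7, replace the open choice of test with one named test for the primary and other binary endpoints: CMH stratified by screening PaO2/FiO2 (200 mmHg or less versus above 200 mmHg), without continuity correction and with its level and sidedness stated. The lower class also takes in a patient at exactly 100. Keep Fisher as a sensitivity analysis for sparse tables. If the SAP already says this, align the protocol sentence with it.

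The cost is one sentence, with no added data or patients. The only statistical downside is about 1 to 2 points of one-sided power against an unstratified CMH if the class turns out weakly prognostic.

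Stratifying the randomisation list by the same class is optional. It adds at most about 2 points of power and is not worth reopening a list that has already been generated.

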3.3. Secondary endpoints

3.3.1. PaO_2/FiO_2 ratio as categorical variable: mild 200 mmHg < $PaO_2/FiO_2 \le 300$ mmHg; moderate 100 mmHg < $PaO_2/FiO_2 \le 200$ mmHg; severe $PaO_2/FiO_2 \le 100$ mmHg.

- 3.3.2. For patients already on mechanical ventilator at time of randomization, the number of days on ventilator after randomization.
- 3.3.3. For patients not on mechanical ventilator at time of randomization, the number of days not requiring invasive mechanical ventilation (i.e., ventilator-free days).
- 3.3.4. PaO_2/FiO_2 ratio as continuous variable.
- 3.3.5. Resting SpO₂ adjusted by FiO₂.
- 3.3.6. Change in oxygen supplementation requirements.
- 3.3.7. Quantitative and qualitative assessment of pulmonary lesions by chest HRCT scans at baseline and at day 14 and week 12.
- 3.3.8. Time to hospital discharge.
- 3.3.9. Time to all-cause mortality up to 28 days.
- 3.3.10. Proportion of patients discharged from ICU and alive within 28 days.
- 3.3.11. Proportion of patients alive within 28 days.

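### Section 4.7 names Kaplan-Meier and Cox for discharge and ventilation without saying how deaths are handled; endpoints 3.3.3 and 3.3.2 are also poorly defined

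*Protocol*

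**What the plan says.** Section 4.7 gives one method for three outcomes: "Analysis of the time to mechanical ventilation, time to all-cause mortality, and time to hospital discharge, respectively, will be undertaken by plotting Kaplan-Meier curves". It adds that "Hazard ratios will be estimated using the Cox proportional hazards model", with two-sided 95% intervals, and closes the paragraph with "Other statistical methods will be applied, as appropriate". It does not mention how death enters the two non-fatal outcomes.

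In section 3.3 the discharge endpoint (3.3.8) reads in full "Time to hospital discharge", with no follow-up limit. Time to mechanical ventilation is analysed in 4.7 but is not listed in 3.3. Endpoint 3.3.3 is "For patients not on mechanical ventilator at time of randomization, the number of days not requiring invasive mechanical ventilation", labelled ventilator-free days. Its definition has no window and no rule for death. Endpoint 3.3.2 is "For patients already on mechanical ventilator at time of randomization, the number of days on ventilator after randomization".

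For continuous endpoints, 4.7 says "Analysis of continuous endpoints will be conducted using analysis of covariance (ANCOVA) model with baseline value as a covariate", together with relevant prognostic factors.

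On eligibility, 4.3 excludes "Invasive mechanical ventilation at screening", and 4.1 describes the enrolled patients as not being on invasive ventilation. The Schedule of Events allows screening up to 72 hours before Day 1. It records oxygen and ventilation needs up to Day 14 only, and only until discharge from the ICU/CCU.

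**The concern.** Death permanently removes a patient from the chance of being discharged or ventilated. The rationale in 1.6 names death as a possible outcome, and 3.3 follows it to 28 days, so this will happen in the trial. Censoring a death treats that patient as someone who would later have been discharged at the same rate as those still in hospital. The resulting curve is too high as a statement of how many patients go home, and the excess is larger in the arm with more deaths.

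The ventilator-free-day count has a related gap. Unless death is scored, a patient who dies early without being intubated may rank level with, or above, a survivor. The protocol deals with this elsewhere: the responder definition in 3.2 and 4.6 requires the patient to be alive, and so does 3.3.10.

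Endpoint 3.3.2 describes a group that the eligibility text is meant to keep out.

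**Working it through.** **Discharge.** The protocol gives no rate for discharge or death, so there is no stated figure to reproduce. All rates below are assumptions: a constant daily discharge hazard h_d of 0.04 or 0.06, and 28-day mortality of 10%, 20% or 30%.

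- With deaths censored: 1 − KM(28) = 1 − exp(−28·h_d).
- True probability of discharge: CIF(28) = h_d/(h_d + h_m) × [1 − exp(−28·(h_d + h_m))].
- The death hazard h_m is solved so that h_m/(h_d + h_m) × [1 − exp(−28·(h_d + h_m))] equals the assumed mortality.

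Example: for h_d = 0.04, 28 × 0.04 = 1.12 and 1 − exp(−1.12) = 67.4%. With h_m = 0.015, the sum is 0.055 and 28 × 0.055 = 1.54. Then (0.04/0.055) × [1 − exp(−1.54)] = 57.1% discharged, with 21.4% dead.

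| h_d per day | 28-day mortality | h_m per day | 1 − KM | CIF | Excess (points) |
|---|---|---|---|---|---|
| 0.04 | 10% | 0.0064 | 67.4% | 62.7% | 4.7 |
| 0.04 | 20% | 0.0138 | 67.4% | 57.8% | 9.5 |
| 0.04 | 30% | 0.0228 | 67.4% | 52.7% | 14.6 |
| 0.06 | 10% | 0.0080 | 81.4% | 75.1% | 6.3 |
| 0.06 | 20% | 0.0175 | 81.4% | 68.6% | 12.8 |
| 0.06 | 30% | 0.0291 | 81.4% | 61.8% | 19.6 |

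The excess is taken before rounding. With no deaths the two quantities agree.

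**Between arms.** Suppose both arms have h_d = 0.04, with mortality 10% in one and 30% in the other. With deaths censored, both curves reach 67.4% and the Cox ratio is 1.0. The actual discharge probabilities are 62.7% and 52.7%, a gap of 10.0 points.

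**Same tools, with a rule for deaths.** Take 100 patients followed to Day 28 with 57.8 discharged, 20 dead and 22.2 still in hospital. If the dead stay in the risk set to Day 28, 1 − KM is 57.8/100, which is the cumulative incidence. The curve depends on the rule for deaths, not on the choice of Kaplan-Meier.

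**Ventilator-free days.** Assume a 28-day window and a never-ventilated patient who dies on day 5. The score is about 4 to 5 if only days alive count, 28 if days after death count as unventilated, and 0 if death is penalised. A survivor ventilated for 24 days scores 28 − 24 = 4. The text does not say which rule applies. Nor does a count of days after randomisation have a baseline value to enter as the ANCOVA covariate.

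**Endpoint 3.3.2 against eligibility.** 3.3.2 needs a patient on a ventilator at randomisation. 4.3 excludes invasive ventilation at screening, and 4.1 says enrolled patients are not on it. What remains is the patient intubated in the gap of up to 72 hours between screening and Day 1, and even that patient does not fit 4.1.

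**The case against.** The strongest reply is that the protocol nowhere says deaths are censored. Censoring rules commonly belong in the SAP, which is not shown, and 4.7 leaves room for other methods. This stands: a reader might infer that the protocol prescribes a biased analysis, but it prescribes Kaplan-Meier and Cox and is silent on deaths. As the working shows, one data rule makes the named methods adequate for discharge, so a Fine-Gray model is not needed.

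A reader might also infer that the Cox ratio is invalid or that excess mortality would be concealed. Neither follows. With deaths censored, Cox still estimates a valid cause-specific hazard ratio; the error would be to read it as an effect on the chance of discharge. Mortality is reported in its own right in 3.3.9 and 3.3.11, and Kaplan-Meier and Cox suit time to all-cause mortality.

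Early deaths look fully ventilation-free only if days after death are counted; if only days alive count, a day-5 death already scores low. Nor is 3.3.2 strictly empty, given the screening gap and the absence of the word invasive in its text.

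The SAP argument does not dispose of everything. The definitions of 3.3.2 and 3.3.3 are the protocol's own endpoint text, and 4.7 chose the methods while leaving open the rule on which their meaning depends.

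**Conclusion.** The point holds in limited form. If deaths are censored, one minus Kaplan-Meier overstates the probability of discharge by about 5 to 20 points across the assumed range, and the Cox ratio is cause-specific only. These sizes rest on assumed constant hazards, a 28-day horizon and assumed mortality of 10% to 30%; none of the rates comes from the protocol. The same reasoning applies to time to mechanical ventilation, for which no size was calculated.

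Endpoint 3.3.3 is incompletely defined and does not fit the stated ANCOVA. Endpoint 3.3.2 conflicts with 4.1 and 4.3; this part needs no assumption and is the firmest. The primary endpoint and the sample size do not depend on any of this.

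**What to change.** 1. **Discharge:** keep patients who die in the risk set as never discharged to Day 28, and present cumulative incidence. A Fine-Gray ratio is optional, since under this rule Cox gives essentially the same ratio.
2. **Ventilation:** analyse time to the composite of invasive ventilation or death.
3. **Endpoint 3.3.3:** define it in all randomised patients over a stated window, with death scored 0, and analyse it by a rank test stratified by baseline PaO2/FiO2 in place of ANCOVA.
4. **Window for 3.3.3:** either match it to the ventilation data that the Schedule of Events collects (to Day 14, and only until ICU/CCU discharge), or add ventilation start and stop dates to Day 28 to the CRF.
5. **Endpoint 3.3.2:** reconcile it with 4.1 and 4.3, and state how a patient intubated between screening and Day 1 is treated in the analysis.

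The cost is protocol or SAP wording and a little programming. The one addition to data collection is the ventilation dates, if a Day 28 window is chosen. The rules should be fixed before any outcome data are analysed.

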3.4. Safety endpoints

Safety endpoints will be:

- 1.3.4.1. Treatment-emergent adverse events and serious adverse events.
- 1.3.4.2. Treatment-emergent adverse events leading to premature discontinuation of study treatment.
- 1.3.4.3. Hypersensitivity reactions including anaphylactic/anaphylactoid reactions.
- 1.3.4.4. Treatment-emergent laboratory abnormalities
- 1.3.4.5. Assessment of immunogenicity.

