Pamrevlumab is infused undiluted after pooling the contents of the calculated number of vials in an empty infusion bag (total volume of fluid must not exceed 410 mL)

Pamrevlumab must be stored refrigerated (2°C to 8°C) and administered within 24 hours of preparation. Pamrevlumab or placebo infusion solutions are administered by IV infusion, using an infusion set with a 0.2 μ m in-line filter.

Dosing will be based on the weight. The total dose of study drug is not to exceed 4.1g. Study Drug will be administered within 24 hours of preparation if stored 2°C-8°C or within 6 hours if stored at room temperature. Study Drug will be administered by IV infusion, using an infusion set with a sterile, nonpyrogenic, low-protein-binding in-line filter (0.2-micron pore size).

Before and after each infusion vitals and AE assessments will be completed. The first 3 study drug infusions will last approximately 2 hours in duration. If the first 3 infusions are well tolerated, all other infusions will be shortened to 60 minutes in duration. Vital signs and assessment of AEs, including any symptoms of hypersensitivity and anaphylactic reactions, will be observed as follows: 2 hours after the first 3 infusions, followed by 1 hour, if the first 3 infusions were well tolerated.

If a patient experiences a hypersensitivity or anaphylactic reaction, the infusion should be immediately stopped; such a patient should be discontinued from further treatment, and followed for safety, up to 4 weeks after the last infusion.

All study drug is provided by FibroGen. All used and unused vials should be accounted for and drug accountability documentation will be maintained. Used and unused vials can be discarded. Records of destruction will be maintained.

7. Safety

All AEs observed or reported spontaneously during the course of the study will be recorded. Reports of hypersensitivity and anaphylactic reactions will be carefully monitored, including by the FibroGen Drug Safety department, as well as by an independent Data and Safety Monitoring Board (DSMB), as soon as it is assembled. An adverse event is defined as any untoward medical occurrence in a clinical trial subject. The event does not necessarily have a causal relationship with study treatment. The investigator is responsible for ensuring that any adverse events observed by the Investigator or reported by the subject as defined in the study protocol are recorded in the subject's medical record.

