9. SCHEDULE OF EVENTS

ASSESSMENTS	Screening		Treatment											ONLY If EOT = Day 14 ^{2,4}	ONLY If EOT = Day 14 ^{2,4}	Continued Treatment visits for eligible subjects (CTV)	Follow-up			
	Up to 72 hrs prior to Day 1	Day 1 (ba seli ne)	Day 2	Day 3	Day 4	Day 5	Day 6	Day 7	Day 8	Day 9	Day 10	Day 11	Day 12	Day 13	Day 14 ⁴	Day 21 (+/- 2 days)	Day 28 (+/- 4 days)	Dosing Q 3 wks +/- 2 days: Week 5, 8,	Week 12 for all subjects	4 weeks (+/- 7 Days) after last Pamrevlu mab dose
Informed consent	Х																			
Eligibility criteria	Х																			
Medical History	Х																			
Demographic information	Х																			
Physical examination	Х																			
Vital signs ³	Х	X1	Х	Х	Х	Х	Х	X ¹	Х	Х	Х	Х	Х	Х	X ¹			X ¹		
ECG	Х																			
Chest HRCT	Х														Х				Х	
Laboratory assessments (local)	Х	Х	Х	Х	Х	Х	Х	Х	Х	Х	Х	Х	Х	Х	Х			Х		
Blood samples for Immunogenicity Assessments		Х						Х							Х					Х
Urine pregnancy test ⁶	Х																			
Randomization		Х																		
Concomitant medications	Х	Х	Х	Х	Х	Х	Х	Х	Х	Х	Х	Х	Х	Х	Χ	Х	Х	X	Х	Х
Infusion		Х						Х							Х					
Arterial Blood Gases (ABG) ³	Х	Х	Х	Х	Х	Х	Х	Х	Х	Х	Х	Х	Х	Х	Х					
PaO ₂ /FiO ₂ ³	Х	Х	Х	Х	Х	Х	Х	Х	Х	Х	Х	Х	Х	Х	Χ					
Resting SpO ₂ (3 times/day) ³	Х	Х	Х	Х	Х	Х	Х	Х	Х	Х	Х	Х	Х	Х	Х					
Oxygen supplementation Needs ^{3, 5}	Х	Х	Х	Х	Х	Х	Х	Х	Х	Х	Х	Х	Х	Х	Х					
Adverse events	Х	Х	Х	Х	Х	Х	Х	Х	Х	Х	Х	Х	Х	Х	Х	Х	Х	Х	Х	Х
Survival and Hospital Discharge Status																Х	Х		Х	Х

¹On infusion days, vitals taken within 30 minutes prior and 30 min after infusion; otherwise vitals taken daily ²Follow-up visits to be done in person or by phone ³Only measured until subject is discharged from the ICU/CCU. ⁴Subjects ending treatment on Day 14 should be contact by phone or return for a visit on Days 21 and 28 for a vital status check. ⁵Including need for mechanical ventilation including ventilator settings, or supplemental oxygen including mode of oxygen delivery ⁵Only for women of childbearing potential or last menstruation <1 year.

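### Section 6 caps follow-up after a hypersensitivity or anaphylactic reaction at 4 weeks, for safety only, which contradicts the Week 12 visit for all subjects and can remove Week 12 data from the pamrevlumab arm alone

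*Protocol*

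**What the plan says.** The rule in Protocol Section 6 (storage, preparation and use) begins "If a patient experiences a hypersensitivity or anaphylactic reaction, the infusion should be immediately stopped", and continues that "such a patient should be discontinued from further treatment, and followed for safety, up to 4 weeks after the last infusion".

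Other parts of the protocol describe follow-up differently:

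- **Section 4.1:** "A follow-up by visit or phone call will be performed 8 and 12 weeks after the end of the last dose of treatment". No exception is made for patients who stop early.
- **Section 9, Schedule of Events:** one follow-up column is headed "Week 12 for all subjects" and includes chest HRCT and survival and discharge status. A second column falls 4 weeks (+/- 7 days) after the last pamrevlumab dose and includes adverse events, an immunogenicity sample and survival and discharge status. The Day 21 and Day 28 vital-status contacts are limited to subjects whose treatment ends on Day 14.
- **Section 7:** the last immunogenicity sample is at the final visit, 12 weeks after the end of treatment. The schedule places it at 4 weeks.
- **Section 5:** "Reasons for discontinuing study drug treatment, as well as reasons for withdrawing from study, will be captured on CRF". It then says "Reasons for withdrawing the subject from the study may include the following", and the safety item is "Any safety concern in the Investigator's opinion, that precludes further study participation".
- **Section 3.4:** one safety endpoint is "Treatment-emergent adverse events leading to premature discontinuation of study treatment". No passage says which efficacy or survival data are collected after such a stop.

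**The concern.** A site cannot follow a patient for safety only, for at most 4 weeks, and also bring the same patient back at Week 12 for HRCT and survival status. If the site follows Section 6, the Week 12 record is never made, and no later analysis can recover it.

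The comparator is standard of care with no study infusion, so a control patient cannot meet the trigger. Any resulting loss is tied to treatment and to a bad experience on it. The data exposed are the Week 12 HRCT (secondary endpoint 3.3.7), the long-term fibrosis objective (Section 2.3) and the late immunogenicity sample. That sample matters most in patients who reacted.

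A second, narrower gap concerns the 28-day endpoints (3.3.9 to 3.3.11). A patient who stops before Day 14 falls outside the Day 21 and Day 28 contacts.

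**Working it through.** The protocol gives no figure to reproduce here. The check is day arithmetic, followed by a comparison of passages.

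**Inputs.** Infusions on Day 1, Day 7 and Day 14 (Section 4.1); possible continued dosing at Week 5 and Week 8 (schedule), taken as Days 35 and 56; cap of 4 weeks = 28 days (Section 6); Week 12 taken as 12 x 7 = Day 84; 28-day endpoints (Section 3.3); responder criterion taken as a window ending on Day 15; 4-week visit window +/- 7 days (schedule).

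**Step 1. Latest day of follow-up under Section 6** = day of last infusion + 28.

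| Last infusion | Cap ends | Past Day 15? | Past Day 28? | Reaches Day 84? |
|---|---|---|---|---|
| Day 1 | Day 29 | yes | yes | no |
| Day 7 | Day 35 | yes | yes | no |
| Day 14 | Day 42 | yes | yes | no |
| Day 35 | Day 63 | yes | yes | no |
| Day 56 | Day 84 | yes | yes | just |

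Week 12 is reached only if last infusion + 28 >= 84, that is, if the last infusion is on about Day 56 or later. All three core infusions fall short.

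**Step 2. Comparison with Section 4.1.** Follow-up at 8 and 12 weeks after the last dose falls on Days 57 and 85 after a Day 1 stop (1 + 56 and 1 + 84), and on Days 70 and 98 after a Day 14 stop. All lie beyond the cap, whatever the day of the last dose, because 56 and 84 both exceed 28. The same holds for the 12-week immunogenicity sample in Section 7.

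**Step 3. Day 28 status.** A full 4 weeks passes Day 28. However, the Section 6 wording sets a maximum and no minimum, and the scheduled 4-week visit may be 7 days early. After a Day 1 stop the earliest visit is 1 + 28 - 7 = Day 22, which is before Day 28. After a Day 7 stop it is 7 + 28 - 7 = Day 28, which is just adequate. After a Day 14 stop the Day 21 and Day 28 contacts apply. The scheduling gap therefore concerns patients stopped after the Day 1 infusion.

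**Step 4. Size.** The number of patients stopped for a reaction is not given. Assuming 1 to 3 of the 34 planned pamrevlumab patients, 1/34 = 2.9% to 3/34 = 8.8% of that arm's Week 12 records would be missing because of this rule, against none in the control arm. These percentages apply to Week 12 data, not to the responder rate.

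**The case against.** The best defence has four parts.

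1. **Four weeks is itself a scheduled visit.** The schedule has a column 4 weeks after the last dose, and it collects survival status and adverse events. Section 6 may simply point to that visit and leave Week 12 in place. The reading is plausible, but the wording sets an upper limit on follow-up and a site could fairly apply it as one. The ambiguity stands.

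2. **The daily assessments do not depend on dosing.** Oxygen and ventilation needs and the Day 14 HRCT are scheduled with no exemption for patients off drug, and controls receive no infusion at all. This is right: following a patient for safety does not expressly cancel them. It is a reason to say so explicitly.

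3. **Few patients are involved.** Section 7 reports no serious allergic or anaphylactic events in over 600 exposed patients, and says the study would be terminated if signs of serious allergic reactions appeared. This limits the size. It is silent on non-serious reactions, which Section 6 also covers.

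4. **Stronger readings fail.** A reader might infer that every safety stop leads either to withdrawal or to the 4-week cap. It does not: the cap is triggered by hypersensitivity or anaphylaxis only. Section 5 is permissive, records drug discontinuation apart from study withdrawal, and limits its safety item to concerns that rule out further participation. A reader might also take Section 5 to act on one arm, but its items apply to subjects in either arm. Finally, a reader might infer that primary-endpoint and 28-day data are lost, or that early leavers would be counted as responders. A full 4 weeks passes both Day 15 and Day 28, and scoring of early leavers may be set out in an analysis plan that is not shown. On those data there is at most a risk.

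**Conclusion.** The contradiction is real. The Section 6 cap cannot be squared with Week 12 for all subjects, with follow-up at 8 and 12 weeks after the last dose, or with the 12-week immunogenicity sample. Section 7 and the schedule also disagree on when that sample is taken. Followed literally, Section 6 removes Week 12 HRCT and survival status in the pamrevlumab arm only, for any reacting patient whose last infusion precedes about Day 56. There is also a narrow gap in 28-day status after a Day 1 stop.

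The conclusion assumes that Week 12 is counted from Day 1 and that sites would apply the cap as written. The number affected is unknown and probably small; the 1 to 3 of 34 used for scale is an assumption. The documents do not show that the primary endpoint is compromised. The point is still worth correcting because uncollected data cannot be restored later and the remedy is cheap.

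**What to change.** - Reconcile Sections 4.1, 6, 7 and 9 on how long, and for what purpose, patients are followed after the last infusion, including the timing of the last immunogenicity sample.
- State in Sections 5 and 6 that stopping study drug is not in itself withdrawal from the study. Patients who are off drug but remain in the study keep the non-infusion outcome assessments already scheduled: oxygen and ventilation status, Day 14 HRCT, Day 28 vital status and the Week 12 visit.
- Extend the Day 21 and Day 28 status contacts to patients who stop before Day 14.
- Leave unchanged the investigator's discretion to withdraw a patient for safety and the clinical rules for stopping drug.

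The cost is a wording amendment and a few additional status contacts, which may be by phone. The assessments already exist in the schedule. The downside is that a few off-drug patients stay in follow-up.
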